#### 12.1.2 Study Endpoints:

The primary endpoint is objective response based on RECIST 1.1 criteria. Response criteria and categories are defined in detail in Sections [10.1.1-10.1.4](#).

Secondary endpoints include toxicity, time to response (TTR), response duration (RD), progression free survival (PFS), and overall survival (OS). Definition, assessment, and reporting of toxicity (adverse events) may be found in Sections [6.1](#), or [10](#). TTR, RD, PFS, and OS are defined in Sections [10.2.1](#), [10.1.5](#), [10.1.6](#), and [10.2.2](#), respectively.

Exploratory endpoints include metabolic response by PET/CT scan, and several laboratory biomarkers listed in [Section 1.3](#) (Exploratory Objectives), and described in [Section 8](#) and in the [Appendix D](#).

## 12.2 Sample Size/Accrual Rate

We anticipate an accrual rate of 1-2 ACC patients/month from the 10 organ dysfunction working group institutions combined. That would yield an expected combined accrual rate of 12-24 patients/year. At that rate, 12 r-e patients should be accrued in 6-12 months. Allowing for up to 12 additional months for the discovery of late responders, a Stage 1 interim analysis result should be obtainable within 18-24 months from the time the first patient begins treatment.

If Stage 2 is needed (i.e., an additional 17 r-e patients), that should take an additional 9-17 months of accrual, plus up to 12 additional months for the discovery of late responders. Thus, a final analysis result at the end of Stage 2 (if Stage 2 is needed) should be obtainable within 39-54 months from the time the first patient begins treatment.

## 12.3 Stratification Factors

None, as this is a single sample Phase II trial. Any stratification of interest can be performed at the time of statistical analysis, after the study data have been collected.

### 12.3.1 Gender and Minority Accrual Estimates

| Phase II Study: Stage 1 / Stage 2 Accrual Estimates |                   |   |              |   |              |
|---|-------------------|---|--------------|---|--------------|
| Ethnic Category  | Sex/Gender |   |              |   |              |
|   | Females    |   | Males |   | Total |
| Hispanic or Latino  | 0                 | + | 0            | = | 0            |
| Not Hispanic or Latino  | 7 / 18            | + | 5 / 11       | = | 12 / 29      |
| Ethnic Category: Total of all subjects                     | 7 / 18 (A1)       | + | 5 / 11 (B1)  | = | 12 / 29 (C1) |
| Racial Category  |                   |   |              |   |              |
| American Indian or Alaskan Native                                 | 0                 | + | 0            | = |              |
| Asian   | 0                 | + | 0            | = |              |
| Black or African American   | 1 / 2             | + | 0            | = | 1 / 2        |
| Native Hawaiian or other Pacific Islander                         | 0                 | + | 0            | = |              |
| White   | 6 / 16            | + | 5 / 11       | = | 11 / 27      |
| Racial Category: Total of all subjects                     | 7 / 18 (A2)       | + | 5 / 11 (B2)  | = | 12 / 29 (C2) |
| (A1 = A2)   |                   |   | (B1 = B2)    |   | (C1 = C2)    |

## 12.4 Analysis of Secondary Endpoints

There are 5 Secondary Objectives:

- 1) To characterize the safety and tolerability of vorinostat in this patient population
- 2) To assess the time to response (TTR)
- 3) To assess the response duration (RD)
- 4) To evaluate progression free survival (PFS)
- 5) To assess overall survival (OS)

Secondary Objective 1 concerns toxicity and adverse events, hence will involve categorical variables. They will be tabulated via frequency distributions, and also dichotomized to report the proportion (and percentage) of patients experiencing a specified level (e.g., Grade 3-4) of toxicity. Analysis of these proportions (i.e., rates) will include both point and 90% confidence interval (CI) estimates, with the CI estimates calculated via Wilson's method. The 90% confidence level is appropriate for either the Stage 1 sample size (n=12) or even the Stage 2 sample size (n=29) planned for this Phase II trial.

Secondary Objective 2 concerns TTR, which is a continuous variable not subject to censoring. It will be summarized descriptively, reporting N, median, mean, standard deviation (SD), standard error (SE), minimum, maximum, and 90% CI for the mean calculated from the SE and asymptotic Normal distribution theory.

Secondary Objectives 3-5 concern censored time-to-event (TTE) endpoints. Their distribution will be estimated using standard survival analysis techniques, and the Kaplan-Meier (K-M) method. From the K-M life tables, both point and 90% CI estimates of various statistics of interest can be calculated (e.g., median, 6-month event-free rate, 12-month event-free rate, etc.). Statistical graphs of each K-M curve (with 90% CI lines) will be generated for visual display of these censored TTE endpoints.

There are 7 Exploratory Objectives:

- 1) To assess the association between a metabolic response by PET/CT after one cycle of chemotherapy and subsequent best tumor response according to standard anatomic response evaluation criteria (RECIST).
- 2) To assess the association between a metabolic response by PET/CT after the first and second chemotherapy cycle and PFS.
- 3) Flow sort diploid, aneuploid, and tetraploid populations of tumor cells from FFPE tissue blocks from patients who benefited from SAHA therapy and from patients who did not demonstrate a durable benefit.
- 4) Profile the genomes of each cell population using oligonucleotide CGH arrays. This will confirm the identification of tumor populations in each sample and provide genomic landmarks

for NGS analysis.

5) Perform whole exome analysis of the sorted tumor population and matching germ line sample for each of the patients. The combined aCGH and exome data will be mined to identify genes and pathways that are targeted by select somatic events in each of the patient subsets

6) To assess stable disease duration (SDD).

7) To assess the association between response to vorinostat treatment and HR23B on tumor paraffin blocks.

Exploratory Objective 1 concerns the potential association of PET/CT response (magnitude of decrease in SUV after 1 treatment cycle) with clinical response by RECIST 1.1 criteria. Percent change in SUV ( $\Delta$ SUV) is a continuous variable, whereas objective response is a categorical (typically, binary) variable. First, we will use receiver operator characteristic (ROC) curve analysis to determine the optimal cutoff in the distribution of  $\Delta$ SUV, in relationship to objective response (yes/no). That will allow us to define “PET response”. We will also compare the descriptive statistics of the  $\Delta$ SUV distribution in the RECIST responders vs non-responders. At Stage 1 (n=12), the association of  $\Delta$ SUV with subsequent best tumor response will be explored in a simple 2 x 2 contingency table, with point and 90% CI estimates of objective response rates among the patients with vs. without PET response. Descriptively only, we can then examine the point and CI estimates to see if there is a hint of any association. At Stage 2 (n=29), we would repeat the same descriptive, exploratory investigation, and then determine what, if any, additional statistical analysis might be appropriate. For example, that might involve exact logistic regression to model the log-odds of later objective response as a function of only one predictor: early PET response (yes/no). This exact logistic modeling investigation would still be viewed as exploratory only, but would yield a point and 90% CI estimate of the odds ratio for response.

Exploratory Objective 2 concerns the potential association of PET/CT response (magnitude of decrease in SUV after 1 treatment cycle) with censored PFS. “PET response” (yes/no) will be determined as just described above for Exploratory Objective 1. At Stage 1 (n=12), to explore the potential association of PET/CT response with length of censored PFS, we will use the Cox proportional hazards model. This analysis will focus on the length of PFS after the second PET/CT scan, and will be exploratory only. The goal would be to determine if there is any hint of a potential positive association in the hypothesized *direction*, i.e., is the hazard ratio (HR) < 1 or not for patients with an early PET/CT response. At Stage 2 (n=29), we would repeat the same Cox model investigation, but pay more attention to the magnitude of (HR), its precision (i.e., half-width of its 90% CI), but not its statistical significance (i.e., p-value). Again, this Cox modeling investigation would still be viewed as exploratory only. A similar analysis will be performed utilizing the third PET/CT scan, taken after 2 treatment cycles, at day 56.

Exploratory Objectives 3, 4 and 5 are strictly exploratory and will be reported as descriptive results

Exploratory Objective 6 concerns yet another time-to-event endpoint (SDD), which is defined in [Section 10.1.5](#). The analysis of the censored SDD distribution will use the same approach as described above for [Secondary Objectives 3-5](#).

Exploratory Objective 7 concerns a biomarker (HR23B), measured by immunohistochemistry (IHC). Its expression level will be recorded as: 0, 1+, 2+, or 3+. In light of the small to modest sample sizes for this Phase II trial (either n=12 after Stage 1, or n=29 after Stage 2), we will dichotomize the total staining score (TSS) of HR23B into  $\geq 6$  (“positive”) or  $< 6$  (“negative”).

At Stage 1 (n=12), the association of HR23B’s dichotomized expression level (absence/presence) to objective response (yes/no) can be explored via a simple 2 x 2 contingency table. From the table we can compute the point and 90% CI estimates of response rates among the patients who do vs. those who do not “express” HR23B. The most basic exploratory observation will be the *direction* of the association, i.e., whether the point-estimate of response rate is higher (or lower) among expressers of HR23B. We can also observe the precision in the estimate of the response rate via its CI.

At Stage 2 (n=29), we would repeat the same descriptive, exploratory investigation, and then determine what, if any, additional statistical analysis might be appropriate. For example, that might involve exact logistic regression to model the log-odds of later objective response as a function “expression” of HR23B (yes/no). This exact logistic modeling investigation would still be viewed as exploratory only, but would yield a point and 90% CI estimate of the odds ratio for response.

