## **Methods**

### ***Samples***

Barbara Ann Karmanos Cancer Institute (KCI) has a set of formalin-fixed paraffin embedded (FFPE) tumor blocks or slides from individual ACC patients who were treated with SAHA. A high number of patients had stable disease on treatment over 6 months (median and range), and we observed a partial response in 2 of the patients in this trial. These FFPE samples are well annotated with clinical follow-up and represent highly favorable samples to exploit for advancing improved outcomes in ACC.

This study will use previously collected FFPE tissue blocks or slides from 10 patients (all available samples may be used at a later point) who achieved some benefit from SAHA and patients whose tumors did not demonstrate a therapeutic response. If an entire FFPE block is not available, PI's will request up to 20 unstained slides (10 microns). A deidentified, coded copy of the pathology report will also be sent with the FFPE block or slides.

Whole blood was also collected on most of the patients at the time of enrollment in the original study. Karmanos will send white blood cells from the blood to TGen to serve as patient matched germline DNA. If no blood exists from a selected patient, or the blood was of poor quality, Karmanos study personnel will recontact the patient to obtain new informed consent and draw a new blood sample.

Blood samples will be spun down to remove the white blood cells from the red blood cells. The white blood cell pellet will be snap frozen using liquid nitrogen and stored at -80° until shipping on dry ice to TGen.

All samples and data will be de-identified and coded with a unique study code assigned by Karmanos study personnel. A key linking the patient name to the study code will be maintained and stored by Karmanos study personnel. TGen will not receive any patient identifiable information before, during or after this study is conducted.

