### **10.2 Other Response Parameters**

#### **10.2.1 Time to Response (TTR)**

TTR is measured from the start of the treatment until the RECIST measurement criteria are met for CR or PR (whichever is first recorded). TTR only applies to the patients achieving either PR or CR, and involves no censoring.

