## 12. STATISTICAL CONSIDERATIONS

### 12.1 Study Design/Endpoints

#### 12.1.1. Study Design:

We will use a 2-stage Simon (1989) optimal design to minimize the number of patients to be treated. Complete + partial (CR+PR) rate will be the primary statistical endpoint. We wish to distinguish response rate regions of at most 5% vs. at least 20%. For this 2-stage design its Stage 1 will require 12 response-evaluable (r-e) patients. At least 1 responder in Stage 1 will be needed to justify continuing to Stage 2, which will require 17 more r-e patients (i.e., maximum of N=29 r-e patients for the study). If  $\geq 3$  responders are observed among the final 29 r-e patients, then vorinostat will be considered promising. If  $< 3$ , conclude that vorinostat has insufficient efficacy to justify further study. This design specifies significance level = 0.15, and power = 0.90, and has a probability of early termination (PET) = 0.540 under the null hypothesis. Alpha is relaxed in this design since there are no effective therapies available, but beta is limited to 0.10 to better ensure that we identify vorinostat as a promising therapy, if it truly is one.

In ACC, late responses (by RECIST) may occur; hence we anticipate the need to suspend accrual after 12 r-e patients have been enrolled for Stage 1. Among stable disease patients still on vorinostat treatment, responses could occur as long as one year after treatment started. Should vorinostat have little efficacy, disease progression among the Stage 1 patients will be more rapid, thus limiting the time until study termination can be justified based on the Stage 1 response results.

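### The 90% interval for mean time to response uses large-sample Normal theory on responders only; with 2 to 6 responders its true coverage is about 65% to 84% even if the data are Normal

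*Combined protocol and SAP*

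**What the plan says.** Section 12.4 treats TTR as an ordinary uncensored measurement: "Secondary Objective 2 concerns TTR, which is a continuous variable not subject to censoring". The planned summary is descriptive. It consists of N, median, mean, SD, SE, minimum and maximum, plus a "90% CI for the mean calculated from the SE and asymptotic Normal distribution theory".

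Section 10.2.1 fixes who contributes: "TTR only applies to the patients achieving either PR or CR, and involves no censoring".

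Section 12.1.1 limits how many that can be. The design separates a response rate of at most 5% from one of at least 20%. "Stage 1 will require 12 response-evaluable (r-e) patients"; "At least 1 responder in Stage 1 will be needed to justify continuing to Stage 2"; the ceiling is a "maximum of N=29 r-e patients for the study". Three or more responders among the 29 count as promising. Section 8 (Methods, Samples) states that "we observed a partial response in 2 of the patients in this trial", and Appendix D says the same.

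The documents give no t-based, exact or bootstrap alternative for this interval, and no minimum number of responders below which it would be withheld.

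**The concern.** Asymptotic Normal theory replaces the sampling distribution of the studentized mean by a standard Normal. That is reasonable when the SE is well estimated. Here the SE comes from a handful of values, so a multiplier of 1.645 is too small and the interval too short for its label. The method does not depend on how the trial turns out: the design itself keeps the number of responders small in almost any scenario.

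The plan is more careful elsewhere. Section 12.4 uses Wilson intervals for toxicity rates and proposes exact logistic regression for exploratory odds ratios. TTR rests on responders alone, yet gets the large-sample formula.

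At stake is a published interval for a named secondary objective that claims more precision than the data hold.

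**Working it through.** **1. Reproduce the design, since it fixes how many responders there can be.** Inputs from section 12.1.1: 12 patients in Stage 1, continue if at least 1 responds, 17 more, success if at least 3 of 29 respond, rates 5% and 20%.

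- Probability of early termination at 5%: 0.95^12 = 0.540, as stated.
- Probability of success = sum over x = 1 to 12 of P(Bin(12, p) = x) × P(Bin(17, p) ≥ max(0, 3 − x)). This gives 0.148 at 5% (stated limit 0.15) and 0.9005 at 20% (stated 0.90).

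The design reproduces.

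**2. Number of responders under that design.** Expected number = 12p + [1 − (1 − p)^12] × 17p.

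- p = 0.05: 0.60 + 0.4596 × 0.85 = 0.99.
- p = 0.20: 2.40 + 0.9313 × 3.40 = 5.57.

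| True rate | 0–1 responders | 2–6 | 7 or more |
|---|---|---|---|
| 5% | 68.3% | 31.6% | 0.05% |
| 20% | 7.3% | 57.2% | 35.5% |

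**3. Coverage of mean ± 1.645 SE when TTR is exactly Normal.** With n responders, (mean − true mean)/SE follows a t distribution with n − 1 df, so coverage = P(|t with n − 1 df| ≤ 1.645). Two cases can be checked by hand:

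- n = 2: (2/π) × arctan(1.645) = 0.652.
- n = 3: 1.645/√(2 + 1.645²) = 0.758.

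| n | Coverage of nominal 90% interval | Correct multiplier (t) | t interval width ÷ planned width |
|---|---|---|---|
| 2 | 65.2% | 6.31 | 3.84 |
| 3 | 75.8% | 2.92 | 1.78 |
| 4 | 80.1% | 2.35 | 1.43 |
| 5 | 82.5% | 2.13 | 1.30 |
| 6 | 83.9% | 2.02 | 1.23 |
| 7 | 84.9% | 1.94 | 1.18 |
| 12 | 87.2% | 1.80 | 1.09 |

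Averaged over the two-stage distribution of n, given at least two responders, coverage is 71.0% at a true rate of 5% and 82.6% at 20%. With 0 or 1 responder no SE can be computed.

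**4. Sensitivity to shape.** The documents give no TTR distribution, so both shapes below are assumptions.

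- Exponential TTR: the planned interval covers 59%, 69%, 74%, 76% and 78% for n = 2 to 6.
- Scan-time mix of 50/20/15/10/5% at weeks 8/16/24/36/48, with days uniform within the protocol's windows (day 56 ± 3 days, later scans ± 1 week): 65%, 67%, 74%, 76% and 78%.

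**5. Illustration.** Two responders, at weeks 8 and 36: mean 22, SE 14, planned interval 22 ± 1.645 × 14 = −1.0 to 45.0 weeks. The lower limit is an impossible time.

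**The case against.** The strongest reply is that this hardly matters. TTR is summarized descriptively; N, median, minimum and maximum are already required; with two responders the minimum and maximum are the whole data set, and a printed N of 2 warns any reader. No test, sample size or stopping rule uses the interval. All of that stands, and it limits the weight of the point. It does not make the interval correct: a range labelled 90% still makes a claim about coverage.

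Three stronger readings are tempting, and the documents do not support them.

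- *That coverage is 65% to 84% whatever happens.* That range needs 2 to 6 responders and Normal data. At a true rate of 20% there is about a 35% chance of seven or more responders, where Normal-data coverage is about 85% or better. At 5% the usual outcome is no interval at all.
- *That tied scan dates would often collapse the interval to zero width.* If TTR could take only exact values of 8, 16, 24, 36 or 48 weeks in the mix above, two responders would tie about 32% of the time. But the Schema and section 9 allow scan windows, and TTR can be counted in days. With those windows the figure is about 4% for two responders and 0.3% for three.
- *That the efficacy conclusion is affected.* Section 12.1.1 decides on responder counts alone.

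**Conclusion.** Wrong as written, with a small effect. The Normal-data coverage figures are exact for the stated method and need no assumption beyond Normality and the number of responders. Coverage stays below the nominal 90% throughout the range of 2 to 12 responders, and is 65% at the two responders the protocol reports. Under the two skewed shapes tried it is lower still, roughly 59% to 78% for 2 to 6 responders; those figures depend on the assumed shapes and show direction rather than a precise size. The damage is limited to one of the descriptive summaries of one secondary endpoint.

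**What to change.** In section 12.4, delete the Normal-theory interval for the mean. Replace it with text to this effect: each responder's TTR will be listed, together with N, median, minimum and maximum; a distribution-free (order-statistic) 90% confidence interval for the median will be given only if there are at least five responders.

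The threshold of five follows from the coverage of the minimum-to-maximum interval for the median, 1 − 2 × (0.5)^n: 87.5% at n = 4 and 93.75% at n = 5.

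If an interval for the mean is kept, use the t distribution with n − 1 df and state that it is exact only for Normal data. It does not cure skewness: under the scan-time mix with windows it covers about 71% at n = 2 and 82% to 86% at n = 3 to 6, and under exponential times about 82% to 84% for n = 2 to 6. In the two-responder illustration it runs from 22 − 6.31 × 14 = −66 to 22 + 6.31 × 14 = 110 weeks, which is why listing the times is preferable.

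Cost: one sentence of text. No patients, data collection or decision rules change. The downside is that the interval will be wider or, with fewer than five responders, not shown.

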### **Definition of a Metabolic Response in FDG-PET**

Based on the reproducibility of the FDG-signal in untreated tumors, relative changes of approximately 20% are very unlikely to be due to measurement errors or spontaneous fluctuations of tumor metabolic activity (72,73). These data establish the minimal effect of treatment on tumor metabolic activity that can be assessed by FDG-PET. However, a measurable change in metabolic activity does not necessarily imply that treatment has a beneficial effect for the patient. A recent study evaluated the prognostic implications of a measurable change in tumor glucose utilization in patients with advanced NSCLC, who were treated with palliative platinum-based chemotherapy. A "metabolic response" in PET was prospectively defined as decrease of the SUV of the primary tumor by at least 20%. A total of 57 patients were included in the study and 28 tumors showed a metabolic response after the first chemotherapy cycle. Median progression-free survival of metabolic nonresponders was only 1.8 months versus 5.9 months for metabolic responders. Median overall survival of metabolic responders was 8.4 months and only 5.0 months for metabolic nonresponders (65). The sensitivity and specificity of a metabolic response for prediction of best response according to RECIST criteria were 95% and 74%, respectively.

These data indicate that a measurable change in tumor FDG uptake after the first cycle of chemotherapy is associated with a palliative effect of therapy. These data and the data on the test-retest reproducibility of FDG-PET suggest that a 20% decrease in tumor FDG uptake may be

used to define a metabolic response in patients with NSCLC. However, we will use slightly stricter criteria for a metabolic response in the present study and define a metabolic response as a decrease of tumor FDG uptake by 25%. The rationale for this definition is that the test/retest reproducibility of FDG-PET in a multicenter trial may be lower than previously reported in single-center studies. Therefore, a 20% threshold may not be robust enough for a multicenter trial. Defining a metabolic response as a 25% decrease of tumor FDG uptake makes this study also consistent with previous recommendations by the EORTC (74).

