NGS Analyses Workflow: Once exome sequencing data is generated, we will leverage our substantial bioinformatics and statistics skills, experience, and large-scale computational capabilities to carry out research-objective-specific customized data-analyses. We have several automated workflows that consist of both published and internally developed data analyses tools for processing sequenced data to generate interpretation-ready results. This includes germline results, such as detecting variants, comparisons with a variety of publically available variants datasets (e.g., dbSNP, 1000 genomes, etc.), functional annotation, Ti/Tv ratios, target sequencing efficiency, etc. Further, when both tumor and normal sequencing data is available, we have well-tested sophisticated workflows for somatic variant detection with detailed comparisons with publically available datasets (e.g., COSMIC). Both germline and somatic variants are comprehensively annotated for functional consequences, such as non-synonymous mutations,

frame-shift insertion-deletions. Our workflows are compatible with standard, platform-independent input sequencing data format (e.g., FASTQ format), generate detailed QC and several additional statistical metrics at various stages of data processing, and deliver results that conform to standard output formats, such as BAM (alignments), VCF (variant calls), functional annotation, etc.

HR23B protein levels will be measured by immunohistochemistry (IHC) using published protocols (86). We will use a single thin section slide for all IHC experiments. All assays will be done through TGen's Macromolecular Analyte and Processing Center (MAPC) pending additional funding. In addition a second slide from each patient will be used for further validation of the recurring t(6:9) MYB-NFIB translocation using conventional fluorescent in situ hybridization (FISH) (87). A semiquantitative analysis based upon intensity and frequency of HR23B staining and the type of dermal and epidermal infiltrate will be performed on each biopsy(87). A total staining score (TSS) will be determined out of 13, where a score of greater than or equal to 6 will be considered to be strong HR23B staining. The threshold for differentiating between positive and negative immunostaining will be set at at TSS of equal or higher than 6. This optimal cutoff was determined by the receiver operating characteristic curve (ROC) distribution analysis.

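### Section 12.4 sets the PET-response cut-off from the trial's own few responders, although Section 2.3 fixes it at a 25% fall; the response comparison is then biased towards an association

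*Combined protocol and SAP*

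**What the plan says.** Section 2.3, under the definition of a metabolic response, states that this study will "define a metabolic response as a decrease of tumor FDG uptake by 25" per cent. It gives two reasons: test-retest reproducibility may be worse across several centres, and the threshold agrees with EORTC recommendations. The next paragraph adds ROC curves because another threshold might predict better. Accuracy there is judged by a 95% interval for the area under the curve (AUC).

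Section 12.4 does not mention 25%. For Exploratory Objective 1, "we will use receiver operator characteristic (ROC) curve analysis to determine the optimal cutoff in the distribution of" the percent change in SUV against objective response, and this cut-off defines PET response. The result goes into a 2 x 2 table with 90% intervals for response with and without PET response, at n = 12 and again at n = 29. At n = 29 an exact logistic model is given as one possible further analysis. For Exploratory Objective 2, PET response "will be determined as just described above for Exploratory Objective 1" and enters a Cox model for PFS.

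On HR23B (Exploratory Objective 7), Section 12.4 says "Its expression level will be recorded as: 0, 1+, 2+, or 3"+, but splits a total staining score at 6. Appendix D describes that score as out of 13, from a semiquantitative analysis of staining intensity and frequency in which "the type of dermal and epidermal infiltrate will be performed on each" biopsy.

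**The concern.** The document holds two definitions of PET response, and the analysis section uses the one chosen from the data. A cut-off picked because it best separates responders from non-responders will appear to separate them in those same patients, whether or not SUV change carries information. The 90% intervals take no account of the search. Section 12.4 gives no optimality criterion, no optimism correction and no validation.

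The stated purpose is to look for a hint of association with response and, for PFS, for a hazard ratio below 1. Choosing the cut-off from the data distorts exactly that kind of reading. With very few responders the distortion is large, and with none the cut-off cannot be computed. A favourable table could then be taken as support for FDG-PET as an early marker in adenoid cystic carcinoma (ACC).

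**Working it through.** **1. How many responders the ROC will have.** Section 12.1.1 states: "We wish to distinguish response rate regions of at most 5% vs. at least 20" per cent. It has 12 patients in Stage 1 and continues if at least 1 responds; the maximum is 29 and at least 3 responders are needed. It adds: "This design specifies significance level = 0.15, and power = 0.90".

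- P(success) = Σ over x = 1..12 of P(X₁ = x) × P(X₂ ≥ 3 − x), with X₁ ~ Bin(12, p) and X₂ ~ Bin(17, p). This gives 0.148 at p = 0.05 and 0.9005 at p = 0.20, so the plan's figures are reproduced.
- P(no responder among 12) = 0.95¹² = 0.540, which matches the plan's "has a probability of early termination (PET) = 0.540 under the null hypothesis" (there PET means early termination). At p = 0.20 it is 0.80¹² = 0.069.
- Expected responders: 12 × 0.05 = 0.6 to 12 × 0.20 = 2.4 in Stage 1, and 29 × 0.05 = 1.45 to 29 × 0.20 = 5.8 at the maximum.
- Section 8 and Appendix D report two partial responses in this trial.

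**2. One responder in 12, by hand.** Assume that SUV change is unrelated to response, all patients have PET, the Youden index J (sensitivity + specificity − 1) is maximised, and both groups must be non-empty. The responder's rank R by size of fall is uniform on 1 to 12.

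- If R ≤ 11, the cut-off falls just below the responder. The response rate is 1/R with PET response and 0 without, and J = (12 − R)/11.
- If R = 12, the best available split gives 0 with and 1/11 without, and J = −1/11.
- Mean rate with PET response = (1 + 1/2 + … + 1/11)/12 = 3.020/12 = 25%.
- Mean rate without = (1/11)/12 = 0.8%.
- Mean J = (66/11 − 1/11)/12 = 0.49.

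The true rate is 1/12 = 8% in both groups.

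**3. Other cases.** These are simulations under the same assumptions, 20,000 data sets each.

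| Responders / n | True rate | With PET response | Without | Mean J |
|---|---|---|---|---|
| 1/12 | 8% | 25% | 1% | 0.49 |
| 2/29 | 7% | 19% | 1% | 0.38 |
| 3/29 | 10% | 23% | 3% | 0.32 |
| 6/29 | 21% | 36% | 10% | 0.25 |

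A separate run without the non-empty rule gives 27% vs 0%, 19% vs 1%, 24% vs 3% and 37% vs 9%. Across the scenarios in that run (1 or 2 responders in 12; 2, 3, 4 or 6 in 29), the association points in the hypothesised direction in 91–97% of null data sets and never in the opposite one. With the closest-to-(0,1) criterion instead of Youden, mean J is 0.20–0.50 and the direction is favourable in 84–92%.

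**4. Fixed cut-off, same null.** The share of patients passing the 25% rule is not in the documents; 20%, 35% and 50% were tried. Mean J lies between −0.004 and 0.007, and mean response rates agree with and without PET response (for example 10.3% vs 10.3% at 3/29).

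**5. Carry-over to PFS.** The cut-off is chosen on response, so it reaches the Cox model only through a link between response and PFS. The documents give no such figure. If responders are assumed to have 2 or 4 times the mean PFS of non-responders, and SUV change is unrelated to either, the median hazard ratio is 0.62–0.88 and falls below 1 in 60–79% of data sets. With a fixed cut-off (35% passing) it is 1.01–1.08, below 1 in 46–50%.

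**6. HR23B, side by side.** A score recorded on a 0 to 3+ scale cannot reach 6. The 13-point score can, but one of its described elements refers to dermis and epidermis, and Appendix D links the score to skin biopsies from cutaneous T-cell lymphoma. No adaptation to ACC tissue is described.

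**The case against.** The plan calls this work descriptive and exploratory, and sets the p-value aside in the Stage 2 Cox analysis. No stopping rule, primary or secondary endpoint or patient decision rests on it, and PET is optional and depends on funding. Section 2.3 itself plans ROC curves. Two planned summaries need no chosen cut-off and are free of this bias: the AUC with its interval, and the comparison of SUV change between responders and non-responders. With one or two responders, a table at 25% would also say little. All of this stands, and it limits the weight of the point. It does not remove the conflict between Sections 2.3 and 12.4. Nor does the exploratory label protect a search for a hint or a direction, because that is what the data-chosen cut-off biases.

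Several stronger readings are tempting but not supported:

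- A reader might infer that an odds ratio from the tuned cut-off is a planned result. Section 12.4 offers exact logistic regression only as an example of what might be done.
- A reader might infer that the Cox model is tuned to PFS. It is not; any bias there depends on the response-PFS link.
- A reader might infer that the HR23B cut-off has the same fault. It does not: the value 6 is fixed in advance, and Appendix D describes its ROC derivation as already done.
- A reader might infer that ACC tissue cannot be scored for HR23B, or that positives will be under-called. Intensity and frequency can be scored in any tissue. The item weights are not given, so the amount of any under-calling is unknown.

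**Conclusion.** The point holds for PET response. Section 12.4 replaces a reasoned, pre-specified definition with one fitted to the outcome it is then compared with, in the same patients. Under no association this gives average apparent differences of roughly 18 to 26 percentage points in the four cases tabulated, where the expected difference should be zero. The size rests on the Youden criterion, PET in every patient and the assumed number of responders; the direction was the same under the alternative criterion tried. Bias in the PFS hazard ratio is conditional on a response-PFS link. If nobody responds, no ROC cut-off exists (54% at n = 12 if the true rate is 5%), and Objective 2 then has no PET-response variable.

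The consequence is an inflated exploratory estimate with intervals that ignore the search. It is not a false primary conclusion. The HR23B inconsistency is secondary and calls only for reconciliation.

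**What to change.** In Section 12.4, define PET response as a decrease of at least 25% in SUV, as in Section 2.3. Use it for the 2 x 2 table, for any exact logistic model and for the Cox analyses at both PET time points. This definition needs no responders and stays the same between stages. Keep the ROC curve with its AUC interval, and the comparison of continuous SUV change, as supplements. If a data-chosen cut-off is shown, name the criterion, label the result as optimistic and base no inference on it.

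For HR23B, state in Section 12.4 and Appendix D one score, its range and a cut-off applicable to ACC tissue, before staining is linked to response.

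The cost is wording in Section 12.4 and Appendix D, with no new patients, scans or data. The downside is that 25% may not be the best threshold for ACC; the supplementary ROC curve would still show that.
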